**Table 4.2—2 Summary of Study Schedules and Evaluations**

|                       | Year 2
Month | Year 3±
4 Month | Year 4±
4 Month | Year 5±
4 Month |
|-----------------------|-------------------------------------|---------------------------------------|---------------------------------------|---------------------------------------|
| Physical Exam  | X                            | X                              | X                              | X                              |
| CRST           | X                            | X                              | X                              | X                              |
| QOL (QUEST)    | X                            | X                              | X                              | X                              |
| ET medications | X                            | X                              | X                              | X                              |
| Adverse Events | X                            | X                              | X                              | X                              |
| Exit Form      | X                            | X                              | X                              | X                              |

Note:

1. To enable subject(s) retention in the Long Term Follow-up study as well as to ensure patient welfare and safety (in full compliance with all applicable patient consent regulation(s) and their corresponding IRB approvals), all participating sites should make every effort to maintain frequent contact with subjects (at least 3 to 4 times a year) to encourage visit compliance and keep them engaged for patient retention.

In the event a patient miss their scheduled visit to complete the study visit requirements, sites should at the very least inquire with subject to provide an overall assessment of their safety and of their tremor in full compliance with all applicable patient consent regulations and rights, and or schedule another clinical visit even if it is outside the visit window.

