## **4.1 LTF Follow Up Periods Years 2 – 5 Post Treatment**

The treatment long term safety and effectiveness follow up will be completed annually from Year 2 through Year 5 post treatment under this protocol. It should be noted that at these visits, the CRST assessments will be performed and scored by the site neurologist.

The following evaluations should be performed at Year 2, Year 3, Year 4 and Year 5:

- Review of medications
- Physical exam
- CRST – Assessed by site evaluator
- QUEST questionnaire should be completed by the subject
- Adverse events

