## 5 DATA ANALYSIS PLAN

### 5.1 Safety

Adverse events will be recorded and categorized according to severity, relationship to procedure and relationship to device. All AEs will be assessed for their relationship to the study device or procedure. Standard Code of Federal Regulation definitions for Serious Adverse Events (SAEs) and Unanticipated Adverse Device Effects (UADEs) will be used in assessment of AEs.

It is the responsibility of the investigator to document all AE's occurring during the course of the study. At each visit, the investigator will evaluate AE's. AE's not previously documented in the study will be recorded on the Adverse Event Log within the CRF. The nature of each event, date and time (when appropriate) of onset, outcome, frequency, maximum intensity, action taken, expectedness, and causal relationship will

---

be recorded. AEs already documented in the CRF (i.e., at a previous assessment) and designated as ‘ongoing’, should be reviewed at subsequent visits as necessary. If these have resolved, the documentation in the CRF should be completed including an end date for the event.

Standard Code of Federal Regulation (CFR) definitions for Serious Adverse Events (SAEs) will be used for evaluation of adverse events.

**SAE** [§803.3(aa)(1)] is an injury or illness that:

- causes death
- is life threatening, even if temporary in nature;
- results in permanent impairment of a body function or permanent damage to a body structure; or
- necessitates medical or surgical intervention to preclude permanent impairment of a body function or permanent damage to a body structure.

All AEs (related or unrelated) meeting the criteria for an SAE require notification of the sponsor and the reviewing IRB as soon as possible, with subsequent completion of additional paperwork provided by the sponsor fully documenting the course of the event, all treatments, and final outcome. Initial reporting of an SAE should be made to the sponsor no later than two (2) working days after the PI learns of the incident. AE's that do not affect the safety or overall well-being of the subject, are mild/moderate in nature, are estimated to be temporary in duration even though the exact end date may not be determined *a priori* (e.g., eye twitch increased from baseline) may be presented and discussed with DSMB to determine their final classification status as a serious or non-serious adverse event.

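### In Years 2 to 5 adverse events are scheduled for evaluation only at annual visits, and the 3 to 4 yearly contacts that Note 1 requests carry no adverse event question

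*Combined protocol and SAP*

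**What the plan says.** - **Visits.** Section 4.1 states that long-term follow-up "will be completed annually from Year 2 through Year 5 post treatment under this protocol" and lists adverse events among the evaluations at each of these visits. Section 4.3 gives each visit a window of ±4 months. Table 4.2—2 marks adverse events at Years 2, 3, 4 and 5.
- **When events are evaluated.** Section 5.1: "At each visit, the investigator will evaluate AE's". The same section sets a general duty: "It is the responsibility of the investigator to document all AE's occurring during the course of the study".
- **Contacts between visits.** Note 1 to Table 4.2—2 says that "all participating sites should make every effort to maintain frequent contact with subjects (at least 3 to 4 times a year". It gives two aims. One is retention, with contacts to be made "at least 3 to 4 times a year) to encourage visit compliance and keep them engaged for patient retention"; the other appears in the words "as well as to ensure patient welfare and safety".
- **Missed visits.** The same note says that after a missed visit "sites should at the very least inquire with subject to provide an overall assessment of their safety and of their tremor", and/or schedule another visit even outside the window.
- **Reporting limit.** Section 5.1: "Initial reporting of an SAE should be made to the sponsor no later than two (2) working days after the PI learns of the incident". The same limit, with the same starting point, applies to unanticipated adverse device effects.
- **Endpoint.** Section 2.1.1 makes the frequency and severity of device- or treatment-related complications, from treatment through Year 5, the primary safety endpoint.

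**The concern.** The primary safety endpoint depends on events being asked about. During the first year the schedule in section 4.3 checks adverse events at 1 day, 1 week and 1, 3, 6 and 12 months. After that, a subject who attends every visit has a scheduled inquiry once a year. Section 5.1 asks for each event's onset date, frequency and greatest intensity, and after a year or more these would rest largely on recall. A serious event soon after one visit could stay unknown to the investigator until the next, and the two-working-day rule would still be met.

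Note 1 already asks for contact several times a year and names safety as one reason, but gives no step that would serve that aim. Section 6 lists long-term serious or unexpected events as a specific post-approval question, so ascertainment between visits bears on what the study is meant to answer.

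**Working it through.** The plan states no sample size, power or event rate (section 5.5), so there is no figure to reproduce. The check is arithmetic on visit windows and contact frequency.

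**Inputs.** Visits at months 12, 24, 36, 48 and 60, each ±4 months (section 4.3). Contacts at least 3 to 4 times a year (Note 1).

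**1. Gap between consecutive visits in window**, for visits at 12k and 12(k+1) months:
- Nominal: 12(k+1) − 12k = 12 months.
- Maximum: [12(k+1) + 4] − [12k − 4] = 20 months. Example: Year 2 at month 20, Year 3 at month 40.
- Minimum: [12(k+1) − 4] − [12k + 4] = 4 months.

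A 20-month gap needs an earliest-day visit followed by a latest-day visit, so two adjacent gaps cannot both be 20. At most 2 of the 4 gaps from Month 12 to Year 5 can be that long for one subject.

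**2. One missed visit.** [12(k+2) + 4] − [12k − 4] = 32 months between attended visits. The missed-visit inquiry in Note 1 applies here, so 32 months is not an interval without any planned inquiry.

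**3. Interval if each contact carried a question**, assuming even spacing (Note 1 sets none): 12/3 = 4 months to 12/4 = 3 months. Nominal against nominal, the interval is 12/4 = 3 to 12/3 = 4 times shorter.

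**4. Illustration only.** Assume onset is uniform between inquiries g months apart. The mean delay to the next inquiry is g/2, and the share of events of duration d still present then is min(1, d/g). The durations are assumptions; the documents give none.

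| Interval g (months) | Mean delay (months) | d = 0.5 month | d = 1 month | d = 2 months | d = 3 months |
|---|---|---|---|---|---|
| 20 (extreme) | 10 | 2.5% | 5% | 10% | 15% |
| 12 (nominal) | 6 | 4.2% | 8.3% | 16.7% | 25% |
| 4 | 2 | 12.5% | 25% | 50% | 75% |
| 3 | 1.5 | 16.7% | 33.3% | 66.7% | 100% |

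An event that has ended by the next inquiry is not necessarily lost, because it can be entered from memory with onset and end dates. The table shows how far ascertainment would rest on recall. It does not show how many events go unrecorded.

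**The case against.** The protocol is not silent on safety between visits. The duty in section 5.1 to document events is not limited to visits, Note 1 names welfare and safety, and a missed visit triggers an inquiry. A contact made partly for safety can fairly be read as covering how the subject is. Subjects who have not reached Month 12 keep their closer checks. The reporting limit already starts by whatever route the investigator learns of an event. The endpoint concerns related complications of a one-time procedure, section 6 expects no known device-related serious events in the long term, and lasting deficits can be found at an annual examination.

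Most of this stands, and it limits the point to missing operational detail. But a duty to document does not create an inquiry, and a stated aim without a task leaves each site to decide whether to ask.

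A reader might infer more than the text supports:
- *Sites are obliged to make the contacts.* Note 1 asks for every effort.
- *Events are lost, or Year 2 to 5 incidence is biased downward.* The documents give no rates or durations. Resolved events can be logged retrospectively, and a death is itself a serious event requiring notification. No comparison of later years with Year 1 is planned.
- *The unmonitored gap is 32 months.* That ignores the missed-visit inquiry.
- *Contacts would shorten the interval 5- to 7-fold.* That sets the extreme gap (20/4 = 5, 20/3 = 6.7) against evenly spaced contacts. The like-for-like figure is 3- to 4-fold.

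**Conclusion.** The point holds as an inexpensive improvement to ascertainment of the primary safety endpoint; it is not a defect that undermines the study. Scheduled inquiry in Years 2 to 5 is nominally every 12 months and at most every 20. The contacts already requested could bring the nominal interval to about 3 to 4 months, if they take place and are evenly spaced. The risk is late reporting, and poor recall of onset and intensity, for new or transient related events between visits. Its size cannot be given from the documents.

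**What to change.** 1. In Note 1 to Table 4.2—2, state that each contact includes a brief scripted question on new or changed adverse events, serious events and hospital admissions, entered on the existing adverse event log with contact date and reported onset date.
2. In section 5.1, extend the sentence "At each visit, the investigator will evaluate AE's" to cover each visit and each retention contact. The reporting limit needs no change; the edit ensures that the question is asked.
3. Reconcile what is to be recorded. Section 5.1 covers all adverse events. Section 2.1.1 does not require reporting of events judged not possibly or probably caused by the device. Section 7.2 restricts recording to events related to the disease, device or procedure, yet also has investigators capture all events. Without one rule, sites will not know what to log from a call.
4. In the adverse event tables, show the source (visit or contact) and separate ascertainment before and after the change, because subjects join at different stages of follow-up.

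The cost is a few minutes per contact, a short script, log entries and more minor events recorded. Note 1 ties contacts to consent rules and IRB approvals, so the added question must fit within these. No extra visit or procedure is needed.

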## 5 DATA ANALYSIS PLAN

### 5.1 Safety

Adverse events will be recorded and categorized according to severity, relationship to procedure and relationship to device. All AEs will be assessed for their relationship to the study device or procedure. Standard Code of Federal Regulation definitions for Serious Adverse Events (SAEs) and Unanticipated Adverse Device Effects (UADEs) will be used in assessment of AEs.

It is the responsibility of the investigator to document all AE's occurring during the course of the study. At each visit, the investigator will evaluate AE's. AE's not previously documented in the study will be recorded on the Adverse Event Log within the CRF. The nature of each event, date and time (when appropriate) of onset, outcome, frequency, maximum intensity, action taken, expectedness, and causal relationship will

---

be recorded. AEs already documented in the CRF (i.e., at a previous assessment) and designated as ‘ongoing’, should be reviewed at subsequent visits as necessary. If these have resolved, the documentation in the CRF should be completed including an end date for the event.

Standard Code of Federal Regulation (CFR) definitions for Serious Adverse Events (SAEs) will be used for evaluation of adverse events.

**SAE** [§803.3(aa)(1)] is an injury or illness that:

- causes death
- is life threatening, even if temporary in nature;
- results in permanent impairment of a body function or permanent damage to a body structure; or
- necessitates medical or surgical intervention to preclude permanent impairment of a body function or permanent damage to a body structure.

All AEs (related or unrelated) meeting the criteria for an SAE require notification of the sponsor and the reviewing IRB as soon as possible, with subsequent completion of additional paperwork provided by the sponsor fully documenting the course of the event, all treatments, and final outcome. Initial reporting of an SAE should be made to the sponsor no later than two (2) working days after the PI learns of the incident. AE's that do not affect the safety or overall well-being of the subject, are mild/moderate in nature, are estimated to be temporary in duration even though the exact end date may not be determined *a priori* (e.g., eye twitch increased from baseline) may be presented and discussed with DSMB to determine their final classification status as a serious or non-serious adverse event.

Standard Code of Federal Regulation (CFR) definitions for Unanticipated Adverse Device Effects (UADEs) will be used for evaluation of this type of adverse event.

**UADE** [§812.3(s)] means any serious adverse event on health or safety or any life-threatening problem or death caused by, or associated with, a device, if that effect, problem, or death was not previously identified in nature, severity, or degree of incidence in the investigational plan or application (including a supplementary plan or application), or any other unanticipated serious problem associated with a device that relates to the rights, safety, or welfare of subjects.

Any UADEs will be reported to the Sponsor and to the reviewing IRB as soon as possible. However, in no event must this report be made later than two (2) working days after the PI learns of the incident.

## 5.2 Data Safety Monitoring Board

A Data Safety Monitoring Board will be used to review all AE's on the study. Their role is to evaluate all AE's that occur throughout the study and determine if they are in fact related to the ExAblate, or some other cause. Investigators will monitor all treatments for any AE's, and consider the following questions for AEs in the Test Arm:

- *Was the adverse event serious?*
- *Was the adverse event life-threatening, caused a disability, required or prolonged hospitalization, or caused death?*
- *Was the adverse event device related?*
- *Was the adverse event unexpected?*
- *Is there an unreasonable risk in continuing the trial?*

Adverse Events meeting all the above conditions would require reporting to the FDA, stopping the study pending the results of further investigation, and FDA approval to restart the study.

All adverse events will be assessed for their relationship to the study device or procedure. Standard Code of Federal Regulation (CFR) definitions for SAEs and UADEs will be used in assessment of adverse events.

### **5.3 Efficacy**

Primary effectiveness will be evaluated using the CRST scored by the site assessor based upon patients where unilateral ExAblate thalamotomy was performed. Secondary efficacy will be collected using the QUEST.

### **5.4 Subject Health Status**

The results from the physical exams will be recorded in the CRFs and will be presented.

### **5.5 Statistical Considerations and Sample Size**

There is no statistical consideration or sample size for this study. All ExAblate treated subjects who were treated under ET002 or ET002-CA will be included in this study, starting at the next scheduled study visit date; ET002-CA was FDA approved under IDE Supplement G120246/S07.

### **5.6 Missing Data**

Analyses will be performed on both observed and data with missing values imputed per the method of last observation carried forward (LOCF) where data for missing visits is assigned the value of the previous visit.

NOTE:

All Demographic, Screening, Baseline, Treatment and some amount of Follow-up data are collected under ET002 or ET002-CA and these data will be used in coordination with that collected under this protocol.

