### **3.1.2 Exclusion Criteria**

1. Subjects who have had a subsequent intervention for ET on their treated side.

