#### **4.2 Exit from the study for reason of alternative treatment**

In this study, subjects who opt for alternative treatments for Essential Tremor (not including medication change) at any point in the follow-up period will be exited from the study after completing the required study examinations. The last set of evaluations prior to alternative therapy is considered the last study visit. The reason(s) for study exit will be noted on the Case Report Forms. No analyses of post alternative treatment changes are planned.

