## **In the long-term (5 years), will favorable Composite Tremor/Motor Function scores compared to the baseline be sustainable among the patients who have received the treatment?**

Based on historical outcomes as published in the literature, it is reasonable to believe that the Composite Tremor/Motor Function improvement will be maintained through follow-up. However, because this cohort of subjects is the first group of subjects to be treated using the ExAblate 4000 device and for many investigators, this was the first hands-on experience in using the device, it is reasonable to anticipate that there may be some patients who do not sustain their improvement over the duration of this study. With the accumulation of user expertise in using the ExAblate 4000, it is expected that the composite Tremor/Motor score outcomes will be sustainable over long durations. It is the purpose of this long-term follow-up protocol to capture the very long term data of the composite Tremor/Motor scores for this cohort of subjects.

---

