### 7.1 Criteria for Removal from the Study

The investigator may withdraw subjects from the study as is deemed necessary or deemed to be in the best interests of the subject, such as,

- continued noncompliance with the protocol or study visits,
- severe illness or disability during the study for non-study issues,
- pursuit of subsequent alternative treatment for the same condition, or
- development of intolerable side effects where continued follow-up becomes too burdensome.

In addition, a subject may also choose to exit the study at any time, but will be strongly encouraged to participate in the follow-up visits for safety reasons (continued monitoring of subject safety). Sites should make every effort to contact all subjects for study follow-up to encourage visit compliance. Sites should keep a log of dates of attempted contact and results. After 3 unsuccessful attempts at contact (e.g., by telephone or email) and sending 1 certified letter to solicit their visit compliance a subject may be considered lost to follow-up.

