| ..Lower 95% CI  | 34.3%                                | -14.9%           |                              | 36.5%                                 |                           |
| Upper 95% CI  | 56.3%                                | 36.2%            |                              | 62.1%                                 |                           |
| A negative sign “-“ indicates worsening                   |                                      |                  |                              |                                       |                           |

The safety profile for the pivotal trial cohort demonstrated a rather benign and favorable profile in relation to benefit. Many events were considered Transient and Unrelated and most resolved. The remaining events were Procedure or Thalamotomy related events. All but one were Mild / Moderate in severity. Only 1 serious, related event occurred of

Moderate Numbness/Tingling of the thumb which interfered with the subject's ability to hold a pen and write at work.

This PAS is simply an observational study to collect longer-term safety and durability of treatment effect in the IDE study population all the way out to 5 years.

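### Section 5.6 names only observed-case and LOCF analyses; neither shows what happened to subjects who left, so the Year 5 durability result can err in either direction and a reader cannot tell which

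*Combined protocol and SAP*

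**What the plan says.** Section 5.6 plans results on observed data and results in which the gaps are "imputed per the method of last observation carried forward (LOCF) where data for missing visits is assigned the value of the previous visit". The supplied text states no missingness assumption, repeated-measures model, multiple imputation or sensitivity analysis. Section 5.5 gives no sample size. Section 5.7 refers to the pivotal-study SAP, which is not among the documents, and limits the analyses to site-assessor data.

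On the question to be answered, Section 6 asks whether, at 5 years, "will favorable Composite Tremor/Motor Function scores compared to the baseline be sustainable among the patients who have received the treatment". It adds that "it is reasonable to anticipate that there may be some patients who do not sustain their improvement over the duration of this study". Section 8 says the study exists "to collect longer-term safety and durability of treatment effect in the IDE study population all the way out to 5 years".

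On leaving the study, Section 4.2 says that "subjects who opt for alternative treatments for Essential Tremor (not including medication change) at any point in the follow-up period will be exited". Their last evaluation before that treatment is the final study visit, and "No analyses of post alternative treatment changes are planned". Section 7.1 lists "pursuit of subsequent alternative treatment for the same condition" and intolerable side effects among the reasons for withdrawal. The entry exclusion in Section 3.1.2 is limited by side: "Subjects who have had a subsequent intervention for ET on their treated side". The exit rule in Section 4.2 has no such limit.

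**The concern.** Each analysis rests on an assumption that the study's own text puts in doubt.

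- **LOCF** fixes a leaver's improvement at the last recorded value. If improvement wanes and exit has nothing to do with outcome, LOCF overstates Year 5 improvement. Section 1.1 calls the disease slowly progressive, and Section 6 expects some loss of benefit. The evidence of waning by Month 12 is mixed. The composite goes from 46.9% to 39.6%, but Posture (64.3% to 65.5%), Part C (63.8% to 64.0%) and QUEST (43.2% to 47.1%) do not fall.
- **Observed cases** assume that stayers represent leavers. Exits for alternative treatment or side effects may well be related to outcome, but the direction is not settled. A subject whose tremor has returned may seek further treatment. As Section 4.2 is worded, a good responder who has the other side treated also exits.

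At stake is the answer to a stated PMA question. Section 5.6 also does not say whether visits after exit or death count as missing visits.

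**Working it through.** The plan states no missing-data figure, so there is none to reproduce. As a consistency check, the midpoint of the Month 12 composite interval is (34.0 + 45.3)/2 = 39.65, against the stated 39.6.

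**1. Identity (no assumed rates).** Let m be the share missing at Year 5, S the stayers' Year 5 mean, L the leavers' last observed mean and U the leavers' unseen Year 5 mean. The target is improvement without alternative treatment, and every leaver is carried forward to Year 5.

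- Truth = (1-m)S + mU
- Observed-case result = S, with bias m(S-U)
- LOCF result = (1-m)S + mL, with bias m(L-U)

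Both results are fixed by m, S and L; U appears in neither. Illustration with m = 0.4:

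| S | L | Observed | LOCF | U | Truth | Pattern |
|---|---|---|---|---|---|---|
| 32 | 39.6 | 32.0 | 35.0 | 20 | 27.2 | both overstate |
| 32 | 39.6 | 32.0 | 35.0 | 32 | 32.0 | observed unbiased, LOCF high |
| 32 | 39.6 | 32.0 | 35.0 | 35 | 33.2 | bracket |
| 36 | 30 | 36.0 | 33.6 | 20 | 29.6 | both overstate |
| 36 | 30 | 36.0 | 33.6 | 35 | 35.6 | bracket |
| 36 | 30 | 36.0 | 33.6 | 38 | 36.8 | both understate |

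For example, 0.6 x 32 + 0.4 x 39.6 = 35.04 and 0.6 x 32 + 0.4 x 20 = 27.2. Identical pairs of tables fit different truths.

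**2. LOCF bias under random exit.** With exit rate h per year at Years 2 to 5 and waning of w points per year after Month 12, a subject first missing at Year 2, 3, 4 or 5 is carried 4, 3, 2 or 1 years. The bias is w x h[4 + 3(1-h) + 2(1-h)^2 + (1-h)^3].

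| h | Retained at Year 5 | Bracketed sum x h | w = 2 | w = 4 |
|---|---|---|---|---|
| 3% | 89% | 0.29 | +0.6 | +1.2 |
| 7% | 75% | 0.65 | +1.3 | +2.6 |
| 12% | 60% | 1.06 | +2.1 | +4.3 |

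With w = 0 the bias is zero. Observed cases are unbiased throughout.

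**3. Exit related to outcome (simulation).** The Month 12 half-width is 5.65. Dividing by t(55) = 2.004 gives an SE of 2.82, and multiplying by the square root of 56 gives an SD of 21.1. Assumed: between-subject SD 17 and residual SD 12.5 (which combine to 21.1), slope SD 2 per year, waning 0, 2 or 4 points per year, and exit log-odds of 0.5 or 1 per SD of score. The model is maximum likelihood on all observed scores. Bias in points at 7-12% exit per year:

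| Exit mechanism | Observed | LOCF | Model |
|---|---|---|---|
| Random | 0 | 0 to +4.3 | 0 |
| Poor previous score | +1.9 to +6.0 | -2.3 to +3.0 | within 0.1 |
| Poor unseen current score | +2.4 to +7.0 | +0.4 to +5.3 | +0.7 to +2.4 |
| Good score, previous or unseen | about -2 to -7 | about -1 to +6.5 | about 0 (previous) to -2.5 (unseen) |

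Both tables are low when good current scorers leave and there is no waning: observed -2.3 to -7.0, LOCF -0.3 to -1.1. At 3% exit per year, with exit random or related to poor scores, no bias exceeds about 2 points. Other splits of the same SD widen the 7-12% ranges for random and poor-score exit to -3.2 to +5.6 for LOCF, 0 to +7.6 for observed cases and 0 to +3.0 for the model.

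**The case against.** **The study is descriptive.** It has no hypothesis test or sample size, and observed results stand beside LOCF. Exit reasons are recorded. Section 4.3 asks sites to keep frequent contact and, after a missed visit, to ask about tremor or see the subject outside the window. All this stands and limits the severity. But the supplied text gives neither the exit reasons nor the tremor inquiries a role in the analysis.

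**The pivotal SAP may contain more.** This also stands; the point covers the supplied text only. Section 5.6 should still be clear, because it states the rule for this study.

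**The model is not always better.** Its near-zero bias when exit depends on seen scores comes from simulated normal data that suit it. Without waning, LOCF can be closer: under exit on a poor unseen score it errs by +0.4 to +1.1, against +0.7 to +2.4 for the model. LOCF also varies less at N=56. Its root mean squared error was 2.98 against 3.30 for random exit at 7% per year without waning. This stands, but LOCF earns that advantage by assuming durability.

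**Post-exit visits may not be imputed at all.** Section 4.2 ends the study at the last evaluation before alternative treatment, so LOCF may not apply to those exits. In that case such subjects simply drop out of the Year 5 table, and the observed-case assumption applies to them.

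**The anchor may not fit.** The Month 12 figures are ITT, may contain imputed values, and may come from a different assessor. The identity in step 1 does not depend on them.

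A reader might infer that both tables overstate durability, or that they must either bracket the truth or overstate it. The documents support neither reading, because the direction of selection is open and both tables can be low.

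**Conclusion.** The concern holds in a limited form. As far as the supplied text shows, the Year 5 durability result rests on two analyses that both omit the leavers' unseen outcomes. The reader cannot tell whether the truth lies between them, below both, above both, or at the observed-case value. That conclusion follows from the identity and needs no assumed rate.

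The sizes are scenario values. At 7-12% exit per year and 0-4 points per year of waning, observed cases err by about -7 to +7 points and LOCF by about -2 to +6.5. A likelihood model errs by about 0 when exit depends on seen scores, and by up to about 2.5 points either way when it depends on unseen ones. Good retention, near 3% exit per year, would make the matter small. How often each pattern occurs in such a grid depends on the scenarios chosen and says nothing about this cohort.

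It should be fixed before the Year 5 analysis, with medium confidence. It does not invalidate the study, and it does not show that the plan will report too favourable a result.

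**What to change.** In Section 5.6:

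1. Make the main durability analysis a likelihood-based repeated-measures model on all observed site-assessor scores from ET002, ET002-CA and this study, with visit as a factor, baseline score, unstructured covariance and no single imputation. Eight visits (Months 1, 3, 6 and 12, Years 2 to 5) need 8 x 9/2 = 36 covariance parameters. Pre-state heterogeneous Toeplitz (8 + 7 = 15) as the fallback if the fit does not converge.
2. State that the model estimates improvement without alternative treatment, in line with Section 4.2. State how scores after death are treated, since a repeated-measures mean otherwise extrapolates past death implicitly. Say whether LOCF covers visits after exit.
3. Keep LOCF and observed cases as secondary tables. At each visit, tabulate the numbers observed, exited by reason (with the side treated), dead and missing.
4. Add one delta-adjusted sensitivity analysis using multiple imputation from the same model, with deltas in both directions (for example -10, -5, 0 and +5 points of improvement), applied by exit reason so that exits for the untreated side are not penalised. In the scenarios with exit on poor unseen scores at 7-12% per year, a delta of 2.9 to 6.1 points removes the model's bias, so -5 and -10 are reasonable. The positive delta covers the case where good responders leave.

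Cost: SAP wording, one extra item on the exit form and a little more analysis of scores already scheduled. The estimate may be less favourable, and its interval somewhat wider than with LOCF: at N=56 and 7-12% exit per year, the simulated SD is about 3.1-3.7 points for the model and 2.7-3.1 for LOCF.
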